## C2 Therapeutics, Inc.

Review of Adverse Events		x	х	Х	Х	х	Х	Х
EGD with cryoballoon ablation	x					X *		
EGD with biopsy protocol						X*	X	Х

#### 3.6 Treatment Procedure

#### 3.6.1 Patient Preparation

The patient should be prepared for the planned endoscopy according to standard hospital procedures for endoscopy under conscious sedation or monitored anesthesia care.

#### 3.6.2 Medication

Pain medication will be administered at the physician's discretion and the use of such medication documented. Acid suppression by double dose PPI will be administered between Informed Consent (Stage 1) and Follow-up Endoscopy (Stage 4,5,6). Other medications will be administered at the physician's discretion and will be documented.

### 3.6.3 Devices and Equipment

In addition to the Investigational System, the following may be required. All devices listed below are to be provided by the site and are available commercially for the indications for which they are proposed in this study.

- Endoscopic system with a therapeutic endoscope (3.7mm or 6.0 MM ID minimum; 100 cm length maximum) and a diagnostic endoscope.
- Materials and supplies used for standard endoscopy according to standard institution practice
- Materials to perform a biopsy.

## 3.6.4 Investigational Procedure

The investigational System must be used according to the manufacturer's IFU provided as **Attachment B**.

#### 3.6.5 Procedure Overview

A summary overview of the procedure is provided below; however, refer to the attached IFU for specific details, warnings, precautions and details steps for system use.

- Review the IFU document for any warnings, precautions or other cautionary statements.
- Prior to use, the investigational System should be examined for defects.
- Insert the balloon catheter into the working channel of the endoscope.
- Visualize and position the balloon in the target treatment zone.
- Prepare the handle per the IFU.
- Connect the balloon catheter to the handle.
- Depress the trigger on the handle for treatment.
- Disengage the trigger when prompted by the console.
- Reposition and retreat if necessary or allow complete balloon deflation and withdrawal the catheter.

### 3.6.6 Disposal of Investigational Device

The Investigational System should be returned to C2 for evaluation. For the return of biohazard product, C2 Therapeutics, Inc. must be contacted prior to product return for handling instructions.

#### 3.6.7 Device Malfunction or Failure

A Risk Analysis was performed by C2 prior to the start of this study. Potential risks were identified and measures taken to reduce the chances for occurrence of each.

Additionally, Performance Testing of the System was conducted in accordance with C2's standardized testing procedures to demonstrate adequate device performance. The combination of the Risk Analysis and the Performance Testing allowed for risks to be identified, performance of the device confirmed, and potential device malfunctions minimized. Refer to the Investigator's Brochure **Attachment A** for additional details.

NOTE: All Adverse Events (AEs) will be followed to resolution. A patient may not be exited from the study until all AEs are resolved or stabilized and an outcome determined.

# 3.7 Study Withdrawal

Subjects may be terminated or withdrawn from the study for the following reasons:

- Subject death.
- Voluntary withdrawal meaning that subject voluntarily chooses not to further participate in the study.
- Loss to follow-up meaning that the subject is or does not return for further follow up.

## C2 Therapeutics, Inc.

NOTE: For those patients considered lost to follow-up (meaning at least 3 attempts to contact the patient are documented and are unsuccessful), the site will, at a minimum, make a concerted effort to confirm that the patient is not deceased (e.g., active search of death indices will be performed to ensure the patient remains alive).

Any study subject who does not participate in a scheduled follow up assessment should be contacted by site personnel to determine the reason. The reason should be determined and documented in the patients study records. If the missed assessment was due to an adverse event (AE), an AE Case Report Form (CRF) must be completed and any reporting requirement met.

All subjects enrolled (including those withdrawn or lost to follow-up) shall be accounted for and documented.

#### 4.0 ADVERSE EVENTS

Adverse events (AEs) may occur during the procedure or during the follow-up phase. **AEs occurring prior to the procedure will be documented in the patient's medical record but will not count as related to the investigational device or procedure.** See the Reporting of AEs section for reporting timelines.

Each AE will be recorded in the corresponding patient's Case Report (CRF). Each AE will be judged by the Investigator as to its relationship and level of relatedness to the investigational System and/or investigational procedure. In addition, the Investigator will identify the date of onset, severity and duration. All AE will be monitored until they are adequately resolved or explained.

#### 5.0 RISK – BENEFIT ASSESSMENT

Upper endoscopy is standard of care for the evaluation of patients who present with foregut symptoms. The risk of participation in this study is similar to that which would be expected from these procedures were the patient not in the study. The most common risks are associated with the introduction of the endoscope and tissue sampling include sore throat, less commonly prolonged bleeding from the sampling site and very rarely injury to the esophagus or stomach that would require surgical repair. The risks associated with the sedation used during endoscopy include local bruising or pain at the IV site, allergic reaction to the medications and over sedation requiring sedation reversal medications and longer post-procedure observation. All patients undergoing endoscopy are monitored with continuous pulse oximetry and vital signs assessment during the procedure. Medications used for conscious sedation are carefully titrated and monitored based on the patients' arousal levels and vital signs.

Anticipated observations and complications are outlined in 5.2.

#### 5.1 Potential Benefits

The simplicity of the Cryoballoon Focal Ablation System allows for potential benefits to the patient, the physician, and hospital including shorter or safer procedures, an easier deployment minimizing the need for anesthesiology, and smaller inventory requirements and no capital equipment improving capital resource utilization. The purpose of this study is to understand the effects of the system on BE epithelial tissue.

Therefore there is no direct benefit of study participation. However, other patients may benefit in the future from the study of the Cryoballoon Focal Ablation System resulting in the development of an easy-to-use alternative to current ablative technologies.

#### 5.2 Potential Risks

The side effects listed below are associated with the investigational procedure as well as endoscopy performed under conscious sedation. The side effects have been categorized as either an observation or a complication. The observations are anticipated as a result of this procedure and are not considered an AE unless they are greater in severity or degree of incidence than anticipated. The complications will be reported as an AE regardless of the degree of severity or incidence.

The observations and complications indicated by an asterisk are solely associated with the investigational procedure. The medical team in charge of this study is aware of these risks and, as with any endoscopy performed, all precautions are taken to avoid these risks. The patient will have the opportunity to discuss any concerns with the medical team.

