#### **Primary Endpoints**

- Device Performance
- Adverse events
- Efficacy for complete elimination (CE) of all esophageal dysplasia
- Efficacy for complete elimination of all BE

All adverse events

Esophageal stricture formation and assessment of clinical dysphagia.

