#### Table 2 - Schedule of Treatments and Assessments

\*Adverse events occurring prior to the procedure will be documented in the patient's medical record but will not count as related to the investigational device or procedure.

\*Treatments: Baseline or initial treatment visit = visit 0; subsequent treatments: 2nd to 5th treatment visits (10 weeks), as needed, up to 12 months from baseline. Treatments only if there is visible residual disease; no endoscopically- visible BE or abnormal squamous mucosa, biopsy will be performed using standardized protocol, beginning at the gastric cardia then the neo-Z line and every 1-2 cm proximal, to sample the previously treated BE areas (according to current standard of care).

Subjects can opt-out of participating in the surveillance phase of the trial after 12 months, if local endoscopic surveillance is preferred.

Adverse events: any patient with pain, dysphagia, fever, or other non-serious adverse event will be called weekly from day 8 to 1 month post-treatment or until AE resolution. Adverse events will be graded and recorded according to standard NIH definitions.

STUDY STAGES $\rightarrow$	Stage 1	Stage 2		Stage 3		Stage 4	Stage 5	Stage 6	
Assessments	Informed Consent/ Baseline Evaluation	Initial Treatment *	Immediately Post-/prior to discharge (up to 12 hours)	1-day Phone Contact (±1 day)	7-day Phone Contact (+/- 1 day)	30-day Phone Contact (+/- 1 day	EGD for treatment or biopsy ( q 8-12 weeks)	EGD for biopsy (endpoint assessment) (12 months)	EGD (24, 36, 48 and 60 months)
Consent	X								
Review of Medical History	x								
Review of Medications	Х	Х	X	Х	Х	Х	X		
Review of General Health	x	х	X	Х	X	X	x		
Physical Exam	X								
Pain and dysphagia Assessment		х	X	X	X	X	x	X	

PROTOCOL# CP-0007/ Version: 8 29April 2019

CONFIDENTIAL

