#### Observations:

- Anxiety
- Bleeding
- Bruising / pain at the IV site
- Change in intestinal function (e.g., constipation)
- Abdominal or chest pain
- Depression
- Difficulty/painful swallowing
- Fever
- Headache
- Lethargy/disorientation/sleepiness
- Nausea and / or vomiting
- Numbness in the mouth, tongue or throat
- Pain
- Sore throat

 Sharma, et al, Balloon-based, circumferential, endoscopic radiofrequency ablation of Barrett's esophagus: 1-year follow-up of 100 patients, Gastrointest Endosc 2007:65:185-95.

PROTOCOL# CP-0007/ Version: 8 29April 2019

<sup>6 Dumot JA, et al, An open-label, prospective trial of cryospray ablation for Barrett's esophagus high-grade dysplasia and early esophageal cancer in high-risk patients, Gastrointest Endosc. 2009 Oct;70(4):635-44.

C2 Therapeutics, Inc.

Bloated feeling

NOTE: If any of the above listed observations are greater in severity or degree of incidence than anticipated, the observation will be considered an AE.

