#### 9.0 DEFINITIONS AND ACRONYMS

#### **Adverse Events**

Adverse Event (AE) - any untoward medical occurrence in a subject (ISO 14155)

NOTE: This definition does not imply that there is a relationship between the adverse event and the device under investigation.

Serious Adverse Event (SAE) - an adverse event that (ISO 14155):

- led to a death,
- led to a serious deterioration in the health of the subject,
- resulted in a life-threatening illness or injury,
- resulted in a permanent impairment of a body structure or a body function,
- required hospitalization or prolongation of existing hospitalization,
- resulted in medical or surgical intervention to prevent permanent impairment to body structure or function,
- Or led to fetal distress, fetal death, a congenital abnormality, or birth defect.

Adverse Device Effect (ADE) - any untoward and unintended response to a medical device (ISO 14155).

NOTE: This includes any event resulting from insufficiencies or inadequacies in the instructions for use or the deployment of the device. This definition also includes any event that is a result of user error.

Serious Adverse Device Effect (SADE) - an adverse device effect that has resulted in any of the consequences characteristic of a serious adverse event or that might have led to any of these consequences if suitable action had not been taken or intervention had not been made or if circumstances had been less opportune (ISO 14155).

Unanticipated Adverse Device Effect (UADE) - any serious adverse effect on health or safety or any life-threatening problem or death caused by, or associated with, a device, if that effect, problem, or death was not previously identified in nature, severity, or degree of incidence in the investigational plan or application (including a supplementary plan or application), or any other unanticipated serious problem associated with a device that relates to the rights, safety, or welfare of subjects (21CFR812.3.s) and (ISO 14155).

NOTE: The occurrence of a diagnostic or elective surgical procedure for a pre-existing condition, unless the condition becomes more severe or increases in frequency, would not be considered procedure or device-related.

C2 Therapeutics, Inc.

Adverse Device Effect (ADE)

See Adverse Events.

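### Section 5.2 removes 15 listed observations from adverse-event status unless they exceed what was anticipated, section 9.0 has no such exception, and nothing says which rule governs the primary endpoint

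*Combined protocol and SAP*

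**What the plan says.** Section 3.1 names adverse events among the primary endpoints, and the same summary also lists "All adverse events". Section 9.0 defines an adverse event as "any untoward medical occurrence in a subject (ISO 14155"), with no carve-out for expected effects.

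Section 5.2 divides side effects into observations and complications. The observations "are not considered an AE unless they are greater in severity or degree of incidence than anticipated", and the note after the list repeats this: "If any of the above listed observations are greater in severity or degree of incidence than anticipated, the observation will be considered an AE". For the other group the rule is unconditional: "The complications will be reported as an AE regardless of the degree of severity or incidence". Two published series (references 5 and 6) are cited at the word *anticipated*.

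Section 4.0 requires each adverse event to go on the case report form, with relatedness, onset date, severity and duration. It sets no such requirement for an observation that is not an adverse event.

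A note to Table 2 reads: "any patient with pain, dysphagia, fever, or other non-serious adverse event will be called weekly from day 8 to 1 month post-treatment". It adds that adverse events are graded and recorded by standard NIH definitions.

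**The concern.** The two definitions give different counts for the same patients, and the endpoint does not say which one it uses. Under section 5.2, a patient with fever or vomiting after treatment may contribute nothing to the primary safety result. Under section 9.0 the same patient has an adverse event.

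The section 5.2 test is also hard to operate. The anticipated level is not printed, and half of the test concerns incidence, which no single event possesses. At stake is the completeness and reproducibility of the tabulated adverse events. The study has no hypothesis (section 7.0), so its safety result is that tabulation.

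**Working it through.** The plan states no adverse-event rate or sample-size calculation on this point, so there is no figure to reproduce. The check compares the texts and adds simple counts.

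**1. Scope.** The observations list in section 5.2 has 14 items from anxiety to sore throat, plus bloated feeling after the page break: 14 + 1 = 15. The complications list has 11. Total 15 + 11 = 26, and 15/26 = 57.7%. Some terms overlap (pain, abdominal or chest pain, pain at the IV site), so this describes the list and not how often events occur.

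**2. Direction.** Let C be complications, O the listed observations, O⁺ the observations judged above the anticipated level, and X other untoward events on neither list.
- Section 9.0 counts C + O + X.
- Section 5.2 counts C + O⁺, and does not exclude X.
- O⁺ is part of O, so every event counted under 5.2 is also counted under 9.0. The shortfall is O − O⁺, which is zero or positive.

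For the share of patients with at least one event, the shortfall is k/n, where k is the number of patients whose only events are exempt observations. At the section 3.1 maximum of n = 100, each such patient removes 1/100 = 1 percentage point, and more if fewer enrol. The documents give no value for k. They report no rates for bleeding, nausea or vomiting, headache or fever.

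**3. Is the anticipated level stated?**

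| Place | What it offers |
|---|---|
| 5.0 | Ranks sore throat and prolonged bleeding in words, then refers on: "Anticipated observations and complications are outlined in 5.2" |
| 5.2 | Cites references 5 and 6; no grade or rate for any item |
| 1.0, preliminary data | Mild pain in 27% immediately and 14% after 2 days; 5.2 does not refer to it |

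**4. Can the test be applied?** The severity limb could be applied to one patient if an expected grade were written down. The incidence limb could not. Incidence is x/n over a group, and x must include every occurrence of the observation. Section 4.0 requires recording only once something is an adverse event, so the count needed to trigger reclassification is not itself required. The reviews after every 10 patients (section 7.3) could examine this but are not given the task. Nor does the protocol say whether earlier occurrences would be reclassified once a threshold was crossed.

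**5. Where a similar test belongs.** Section 9.0 asks whether a serious device effect was "not previously identified in nature, severity, or degree of incidence in the investigational plan". There the test separates unanticipated effects from others. Section 5.2 uses nearly the same test to decide whether an event is an adverse event at all.

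**The case against.** The strongest reply is that *anticipated* has an anchor. Section 5.2 cites two published series, and the Investigator's Brochure and Instructions for Use, not seen here, may hold further figures. It would therefore be wrong to call the standard unanchored. What stands is narrower. Section 5.2 takes no figure from either series and does not say which one governs. By their titles they concern radiofrequency ablation and cryospray.

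A reader might infer that Table 2 contradicts section 5.2 as plainly as section 9.0 does. The documents do not support that. The note calls pain, dysphagia and fever non-serious adverse events without a threshold, but it concerns calls from day 8. Symptoms lasting that long could be read as exceeding what was anticipated. The note is supporting evidence only. Its NIH sentence governs how adverse events are graded, and it does not say which grade is expected.

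A reader might also infer that early discontinuation hinges on this count, because section 8.6 mentions unexpected incidence of known adverse events. That list is discretionary and open-ended, so the inference fails.

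The remaining mitigations are sound. Pain is a secondary endpoint. Pain, dysphagia and odynophagia are collected by questionnaire (section 3.5.3). Table 2 schedules general-health and adverse-event reviews at repeated contacts. Complications always count, and none of the three suspension triggers in section 7.3 is an observation. With one site and the investigator judging each event, variation between assessors is also limited. These points narrow the consequence but do not say which definition the endpoint uses.

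**Conclusion.** The contradiction between sections 5.2 and 9.0 is real and should be fixed. Relative to section 9.0, applying section 5.2 leaves the adverse-event count and the share of patients with an event lower or unchanged. This assumes that a listed side effect is an untoward occurrence. It does not extend to ratios with adverse events in the denominator: the serious share of events could rise.

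The size cannot be determined, and the shortfall is zero if staff follow section 9.0. It would go too far to say that the safety result is understated by a known amount, or that pain and swallowing data are lost. The likely effect is on milder bleeding, nausea or vomiting, headache, fever and similar events, which have no dedicated score.

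**What to change.** Reconcile section 5.2 with its note, the Table 2 note and section 9.0, so that the section 9.0 definition governs the primary endpoint. Replace the exemption and its note with an anticipated yes/no flag on each adverse-event record, alongside severity and relatedness. Tabulate all adverse events for the primary endpoint, and add a second table of those not flagged as anticipated. This keeps the distinction that section 5.2 wants without removing events.

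The preliminary-data section reports 41 Barrett's and 10 squamous patients, 41 + 10 = 51, already treated within this study. Report adverse events separately for patients treated before and after the change, so that two definitions are not pooled unseen. Recover earlier observations from existing questionnaires and source notes where possible; recovery may be incomplete.

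The cost is wording changes, one form field, one extra table, more adverse-event entries and the retrospective search. The reported adverse-event rate may become less favourable.

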#### Observations:

- Anxiety
- Bleeding
- Bruising / pain at the IV site
- Change in intestinal function (e.g., constipation)
- Abdominal or chest pain
- Depression
- Difficulty/painful swallowing
- Fever
- Headache
- Lethargy/disorientation/sleepiness
- Nausea and / or vomiting
- Numbness in the mouth, tongue or throat
- Pain
- Sore throat

 Sharma, et al, Balloon-based, circumferential, endoscopic radiofrequency ablation of Barrett's esophagus: 1-year follow-up of 100 patients, Gastrointest Endosc 2007:65:185-95.

PROTOCOL# CP-0007/ Version: 8 29April 2019

<sup>6 Dumot JA, et al, An open-label, prospective trial of cryospray ablation for Barrett's esophagus high-grade dysplasia and early esophageal cancer in high-risk patients, Gastrointest Endosc. 2009 Oct;70(4):635-44.

C2 Therapeutics, Inc.

Bloated feeling

NOTE: If any of the above listed observations are greater in severity or degree of incidence than anticipated, the observation will be considered an AE.

### Complications:

- Allergic reaction to the medications given
- Cardiac arrhythmia (irregular heartbeats which could be life-threatening)
- Inhalation of gastric secretions (breathing in of fluid in the stomach)
- Infection
- Hemoptysis (coughing up of blood)
- Over-sedation requiring sedation reversal
- Perforation or laceration (small hole or tear) of the esophagus
- Decreased respiration
- Stricture (narrowing of the esophagus)
- \*Ingestion of the fluid in the cryoballoon which may result in discomfort/stomach bloating
- Death

### 5.3 Minimization of Anticipated Risks

All efforts will be made to minimize these risks by System design, selecting investigators who are experienced and skilled in endoscopic procedures, clearly defining eligibility criteria to ensure that only the appropriate patients are enrolled and by ensuring that the treatment and follow-up of the patient are consistent with current medical practice.

Risks are further minimized due to:

- The use of medical grade materials that have a long history of use and have been characterized and tested to assure biocompatibility.
- Biocompatibility testing has been performed and the results were determined acceptable.
- Pre-clinical evaluation including bench testing, analytical testing and animal studies.

